## **6.2 Treatment Cohorts**

Subjects are randomized with the ratio of 1:1 into 2 treatment cohorts to receive acalabrutinib, with or without dexamethasone:

- Cohort 1 (acalabrutinib monotherapy): acalabrutinib 100 mg bid continuously
- Cohort 2 (acalabrutinib + dexamethasone): acalabrutinib 100 mg bid continuously and 40 mg dexamethasone once weekly

## **7. INTERIM ANALYSIS AND EARLY STOPPING GUIDELINES**

No formal interim analysis will be conducted.

## **8. FINAL ANALYSIS AND CLINICAL STUDY REPORT**

The final analysis of primary and secondary efficacy endpoints will occur when last patient enrolled completes the end of Cycle 12, or withdraws for any reason and completes the 30-day follow-up visit, whichever occurs first. The CSR will be written based on the final analysis. The addendum of CSR will be written at the end of trial.

## **9. MISSING VALUES**

### **Missing Safety Data**

Conservative imputation rules will be applied partial dates for AE onset and stop dates, start and end dates of concomitant medication, start date of subsequent anticancer therapy, date of initial diagnosis, and death date. The algorithm for the imputation in Appendices 14.2 will be used. If dates are completely missing, no imputation will be made. Missing safety data other than partial or missing dates will not be imputed.

### **9.2 Missing Efficacy Data**

The method of handling missing data and censoring data is described in the definition for the efficacy endpoints, mentioned at section 14.3.

## **10. STATISTICAL METHODS OF ANALYSIS**

## **10.1 General Principles**

Descriptive statistics will be used to summarize disposition, demographics, baseline characteristics, disease characteristics, prior anticancer therapy, concomitant medication, study drug administration, efficacy and safety outcomes. Descriptive summary of discrete data will be present the sample size and incidence as frequency and percentage. Descriptive summaries of continuous data will be present the sample size, group mean, standard deviation, median, and range.

Confidence intervals (CIs), when presented, will generally be constructed at the 95% level. For binomial variables, the exact method for CIs will be employed unless otherwise specified.

Calculation of time to event or duration of event (e.g., DOR) will be based on actual study day of event rather than nominal visit date.

## **10.2 Subject Disposition**

Subjects are enrolled from 11 study sites of 2 countries. The number of subjects enrolled by region, country, and site will be presented. Subject disposition will be summarized for all enrolled subjects including the following information:

- Subject status on acalabrutinib
- Primary reasons for acalabrutinib discontinuation
- Subject status on the study
- Primary reasons for study discontinuation
- Time on the study

## **10.3 Important Protocol Deviations**

Important Protocol Deviations (IPDs) categories are defined and managed by the study team during the IPD reviews throughout the study before database lock. These definitions of IPD categories, sub-category codes, and descriptions will be used during the course of the study. The final IPD list is used to produce the Summary of IPDs table.

## **10.4 Baseline Data**

Summaries of demographics and baseline characteristics will be presented for subjects in the All-treated population. For continuous variables, n, mean, standard deviation,

median, minimum, and maximum values will be provided. For categorical variables, the number and percentage of subjects in each category will be summarized.

#### **10.4.1 Demographics**

- Sex (Male, Female)
- Age (year, continuous)
- Age category (<65 versus ≥65 years)
- Ethnicity
  - Hispanic or Latino
  - Not Hispanic or Latino
  - Not Reported
- Race
  - American Indian or Alaska Native
  - Asian
  - Black or African American
  - Native Hawaiian or Other Pacific Islander
  - White
  - Other
  - Not Reported
- Country
  - Unites States
  - United Kingdom

#### **10.4.2 Baseline Characteristics**

- Eastern Cooperative Oncology Group (ECOG) performance score
  - 0 = fully active.
  - 1 = restricted in physically strenuous activity
  - 2 = incapable of any work activity
  - 3 = limited self-care
  - 4 = completely disabled
- Height (cm)
- Weight (kg)

#### **10.4.3 Baseline Disease Characteristics**

- Time from initial diagnosis to first dose of acalabrutinib (months)

- Prior anticancer therapy regimens
  - Number of regimens (mean, standard deviation, median, minimum, maximum)
  - Number of subjects with regimens (1-3 regimens,  $\geq 4$  regimens)
- Prior stem cell transplant
- MM stage by International Staging System (ISS) (stage I, II, III [Greipp 2005])
- MM subtypes
  - heavy chain subtypes
  - light chain subtypes
- Serum  $\beta 2$ -microglobulin ( $< 2.5$ ,  $\geq 2.5$  mg/L)
- Serum creatinine ( $< 2$ ,  $\geq 2$  mg/dL)
- Serum Hemoglobin (mean, standard deviation, median, min, max)
- Serum calcium ( $\leq 12$ ,  $> 12$  g/dL)
- IgG (mean, median, min, max)
- IgA (mean, median, min, max)
- Bone marrow cellularity
  - Hypercellular
  - Normocellular
  - Hypocellular

## 10.5 Treatment and Medications

### 10.5.1 Prior Anticancer Therapies

A prior anticancer therapy is defined as a systemic therapy subjects received, either as a single or combination therapy, for the treatment of MM with an end date occurring before the date of first dose of study treatment. Therapies given as a consolidation or for maintenance of a response or remission will not be considered as a separate regimen. The prior anticancer therapy regimens will be summarized.

### 10.5.2 Prior and Concomitant Medications Received for Indications Other Than MM

Concomitant therapy is defined as all medications used on or after the first dose of study drug, through the treatment phase, and through 30 days following the last dose of study drug. Data reported on concomitant medications CRF pages will be used. Medications

started prior to first dose of study drug will be considered as prior treatment. Using this definition, a medication can be classified as both prior and concomitant. The start date and end date will be based on the rules provided in [Appendices 14.2.1](#). Medications with completely missing start and stop dates will be considered as both prior and concomitant medications. Prior and concomitant medications other than antineoplastic agents or other systemic therapies for MM after enrollment will be coded by the World Health Organization (WHO) Drug Dictionary and summarized by Anatomic Therapeutic Chemical Classification System (ATC) level 2 (therapeutic subgroup) and level 5 (preferred term/chemical ingredient).

### 10.5.3 Exposure to Study Drugs

Separate analysis will be performed for acalabrutinib and dexamethasone. Descriptive statistics (n, mean, standard deviation, median, minimum and maximum values) will be used to summarize:

- Duration of exposure (the interval between first dose date and last dose date)
- Actual cumulative dose administered
- Average dose (the ratio of actual cumulative dose administered and Duration of exposure): daily dose for acalabrutinib and weekly dose for dexamethasone
- Relative dose intensities (the percentage of actual cumulative dose to the planned cumulative dose)

The reasons for acalabrutinib dose withholding and reduction will be summarized and presented as the number and percentage of subjects with non-missing data per category.

- Dose withholding of acalabrutinib is defined as missing dose for  $\geq 7$  consecutive days.
- Dose reduction defined as taking lower dose level (100 mg per day) for acalabrutinib for  $\geq 3$  consecutive days.

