3.5.3.2 Dexamethasone

This study will use commercially available dexamethasone tablets for oral administration. At the time of weekly dexamethasone administration, the subject should take the dexamethasone tablets simultaneously with the ACP-196 capsules and with 8 ounces (approximately 240 mL) of water. The dexamethasone tablets should be swallowed intact and subjects should not attempt to chew them or dissolve them in water.

If a dexamethasone dose is missed, it can be taken up to 3.5 days (84 hours) days after the scheduled time with a return to the normal schedule the following week. If the interval of missed dosing has been > 3.5 days (84 hours), the dexamethasone dose should not be taken and the subject should take the next dose at the scheduled time in the following week. The missed dexamethasone dose will not be made up and must be returned to the site at the next scheduled visit.

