3.5.4 Assuring Subject Compliance

During cycle 1, subjects will receive their Day 1, 8, 15, 22, and 28 doses (for Cohort 2 this includes the dexamethasone dose) in the clinic. For treatments that are taken in the clinic, subjects should take the dose from the drug dispensed for them for that particular time period. All other treatments will be taken at home. Subjects will receive a diary to record the specific time each dose was taken and to record reasons for any missed doses.

Subject compliance will be assessed at every visit. The subject will be instructed to bring the diary and any remaining ACP-196 capsules and dexamethasone tablets to the clinic at their next visit. The administrator will review the diary and ask the subject if all of the capsules and tablets were administered. Any remaining or returned capsules and tablets will be counted and recorded as described in Section 7.7. Returned capsules or tablets must not be redispensed to another subject. The study staff will resupply the subject with the correct number of ACP-196 capsules and dexamethasone tablets needed for use until the next visit.

3.5.5Study Treatment Regimen and Dose Modifications3.5.5.1ACP-196

Dose Delays

Treatment with ACP-196 should be held for any unmanageable, potentially study drugrelated toxicity that is Grade \geq 3 in severity. Any other clinically important events where dose delays may be considered appropriate by the investigator must be discussed with the Medical Monitor. Study drug may be held for a maximum of 28 consecutive days from expected dose due to toxicity. Study treatment should be discontinued in the event of a toxicity lasting > 28 days, unless reviewed and approved by the Medical Monitor.

Note: temporary withholding of study drug for as little as 7 days can cause a transient worsening of disease and/or of constitutional symptoms. Refer to Section 3.8 for more information on assessing disease progression under these circumstances.

Dose Modification and Discontinuation

The actions in Table 3-1 should be taken for the following toxicities:

- Grade 4 ANC (< 500/µL) for > 7 days (Neutrophil growth factors are permitted per ASCO guidelines [Smith 2006] and use must be recorded on the electronic case report form [eCRF]).
- Grade 3 platelets in the presence of significant bleeding
- Grade 4 platelets
- Grade 3 or 4 nausea, vomiting, or diarrhea, if persistent despite optimal antiemetic and/or anti-diarrheal therapy

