3.5.5.2 Dexamethasone

This study will use commercially available dexamethasone. Dosing of dexamethasone will be 40 mg once weekly. For subjects who experience intolerable dexamethasone-related adverse effects, dexamethasone may be reduced to 20 mg once weekly.

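### SAP 10.5.3 divides k weekly dexamethasone doses by k − 1 weeks, so a fully compliant subject's average weekly dose reads above 40 mg

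*SAP*

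**What the plan says.** SAP 10.5.3 (Exposure to Study Drugs) lists four quantities. "Separate analysis will be performed for acalabrutinib and dexamethasone", so I take each drug's own first and last dose dates to apply. The relevant lines are:

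- The denominator is given as "Duration of exposure (the interval between first dose date and last dose date").
- The row at issue is "Average dose (the ratio of actual cumulative dose administered and Duration of exposure): daily dose for acalabrutinib and weekly dose for dexamethasone".
- A third row compares delivery with plan: "Relative dose intensities (the percentage of actual cumulative dose to the planned cumulative dose").

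For these rows, "Descriptive statistics (n, mean, standard deviation, median, minimum and maximum values) will be used to summarize".

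The section adds neither a day nor a final dosing interval to the duration, and it does not define planned cumulative dose.

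Protocol 3.5.5.2 sets the regimen: "Dosing of dexamethasone will be 40 mg once weekly". The synopsis restates this as a 40 mg weekly total. Protocol 3.5.5.2 also allows a reduction to 20 mg weekly.

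**The concern.** An average weekly dose should return the protocol dose when a subject takes every dose on time. Here the numerator counts every dose, but the denominator stops on the day of the last one, so the week that the last dose covers is left out. For a twice-daily drug the shortfall is one day. For a weekly drug it is a full week, and it weighs most in short courses.

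What is at stake is how the exposure table reads:

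- Compliant subjects would appear above the protocol dose.
- The maximum would be driven by whoever took fewest doses.
- Subjects with one dose would have no computable value.
- A missed or reduced dose could cancel the excess and look like full delivery.

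The last point matters somewhat more because SAP 10.5.3 summarizes reasons for withholding and reduction for acalabrutinib only. In that section, dexamethasone under-dosing can show only through cumulative dose, average dose and relative dose intensity.

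**Working it through.** **Target.** The SAP prints no computed average dose, so there is no figure to reproduce. The benchmark is the protocol regimen, 40 mg per week.

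**Formulas for k doses of 40 mg exactly 7 days apart.** Cumulative dose is 40k mg. Last dose date minus first dose date is 7(k − 1) days.

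- As written: 40k ÷ (k − 1)
- With +1 day: 280k ÷ (7(k − 1) + 1)
- With +7 days: 280k ÷ 7k = 40.0

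| Doses | As written | Excess over 40 | +1 day | +7 days |
|---|---|---|---|---|
| 1 | undefined (40 ÷ 0) | – | 280.0 | 40.0 |
| 2 | 80/1 = 80.0 | 100% | 560/8 = 70.0 | 40.0 |
| 4 | 160/3 = 53.3 | 33% | 1120/22 = 50.9 | 40.0 |
| 8 | 320/7 = 45.7 | 14% | 2240/50 = 44.8 | 40.0 |
| 12 | 480/11 = 43.6 | 9% | 3360/78 = 43.1 | 40.0 |
| 24 | 960/23 = 41.7 | 4% | 6720/162 = 41.5 | 40.0 |
| 48 | 1920/47 = 40.9 | 2% | 13440/330 = 40.7 | 40.0 |

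**Under-dosing that the rule hides.** Take four scheduled weeks with doses 40, none, 40, 40. As written this gives 120/3 = 40.0; with +7 days it gives 120/4 = 30.0. Doses 40, 40, 20, 20, using the permitted reduction, give the same two figures.

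**Acalabrutinib.** At 200 mg daily for 28 days the written rule gives 5600/27 = 207.4 mg/day, and +1 day gives 5600/28 = 200.0. One extra day is enough for a daily drug but not for a weekly one.

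**Late doses.** Protocol 3.5.3.2 says of a missed dexamethasone dose that "it can be taken up to 3.5 days (84 hours) days after the scheduled time".

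- Two doses 10 days apart: as written, 80 × 7/10 = 56.0.
- Four doses, last one 3 days late: as written 1120/24 = 46.7; +1 day 1120/25 = 44.8; +7 days 1120/31 = 36.1.
- Four doses, last one 4 calendar dates late (84 hours can cross four dates): as written 1120/25 = 44.8; +1 day 1120/26 = 43.1; +7 days 1120/32 = 35.0.

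**Relative dose intensity.** If planned dose comes from the weekly schedule, 40, none, 40, 40 gives 120/160 = 75%, and 40, 40, none, none gives 80/160 = 50%. If planned dose were instead built on the +7 duration, the second pattern would give 80/80 = 100%.

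**Day 28.** Protocol 3.5.4 says that in Cycle 1 "subjects will receive their Day 1, 8, 15, 22, and 28 doses" in the clinic, and adds that for Cohort 2 this includes dexamethasone. Day 28 is 6 days after Day 22. If it is a fifth 40 mg dose, the written rule gives 200 × 7/27 = 51.9 and +7 days gives 200 × 7/34 = 41.2.

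**The case against.** The strongest reply is that the SAP gives a gloss and not a formula, and that its own habit is inclusive counting. Study day (14.1.1) and duration of lymphocytosis (10.6.2) both carry an explicit +1. A programmer might well apply it here, and then the figures are 70.0, 50.9 and 43.1, with no division by zero. That is fair as to size, and both readings should be shown. It does not remove the problem, because one day cannot stand in for a 7-day dosing interval.

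Second, +7 days is not exact. When the final dose is late it understates the dose. For four doses with the last one 4 calendar dates late, even the written rule is nearer to 40 (44.8 against 35.0). This stands. A reader might infer that the +7 rule is always the closest to 40, and the protocol's own missed-dose window shows that it is not. The case for it is that it is exact when dosing is on schedule, where the written rule is always too high.

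Third, changing the duration for the average dose alone would leave a table in which the printed duration and cumulative dose no longer reproduce the printed average. This also stands, and it is why both rows need the same definition.

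Fourth, little depends on the row. No safety or efficacy endpoint in SAP section 4 uses average dose, section 5 tests no formal hypotheses, and cumulative dose and relative dose intensity sit beside it. This is correct and sets the severity.

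**Conclusion.** The point holds as a minor one. The stated rule gives the wrong weekly dexamethasone figure for every compliant subject, and nothing else in the protocol or SAP corrects it. The sizes in the table rest on 40 mg doses, exact 7-day spacing and drug-specific dose dates.

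Three stronger readings should be resisted:

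- The table's maximum will not necessarily be 80 mg/week. That needs a subject with exactly two doses 7 days apart; at 10 days the figure is 56.0. The documents do not report how many doses subjects took, so the shift in the group mean or maximum cannot be computed.
- Relative dose intensity is not shown to be wrong. As written it does not use this interval, and it would be affected only if planned cumulative dose, which is undefined, were derived from it.
- No conclusion on safety or activity changes. The effect is confined to a descriptive exposure row.

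**What to change.** In SAP 10.5.3:

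1. Define duration of exposure as (last dose date − first dose date + 7)/7 weeks for dexamethasone and (last dose date − first dose date + 1) days for acalabrutinib.
2. Use these definitions for both the reported duration and the average dose, so that the printed rows agree.
3. State that planned cumulative dose for relative dose intensity comes from the planned schedule and not from this duration. Otherwise doses missed after the last one taken would disappear.
4. Note that the dexamethasone average is exact at 7-day spacing and approximate when the final dose is late.

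Separately, the Day 28 in-clinic dose in Protocol 3.5.4 and the once-weekly dexamethasone schedule in 3.5.5.2 must be reconciled, so that the planned dose count for Cycle 1 is unambiguous.

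The cost is a few lines of SAP text and one derivation per drug for duration. That derivation and the average dose use only the first and last dose dates and cumulative dose that the section already requires.

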### 10.6 Analyses of Safety Endpoints

Safety analyses will be performed on All-treated population by treatment cohort.

Analyses of adverse events (AEs) will be performed on treatment-emergent AE (TEAE) data, unless otherwise specified. TEAEs are defined as those events with onset or

worsen date on or after the date of first dose of acalabrutinib, through the treatment phase to last dose of acalabrutinib, and within 30 days following the last dose of acalabrutinib, whichever is later. Common Terminology Criteria for Adverse Events (CTCAE) Version 4.03 or higher is used for AE grading.

Treatment-emergent AEs will be summarized in 3 groups: (1) acalabrutinib monotherapy, (2) acalabrutinib + dexamethasone, and (3) crossover from monotherapy to acalabrutinib + dexamethasone therapy. By this grouping method, AEs among subjects assigned to acalabrutinib monotherapy will be reported in group 1 when AEs occurred before crossover, and AEs occurred on/after crossover will be reported in group 3. Treatment-emergent AEs occurred on or after crossover will be summarized in the crossover group. Treatment-emergent AEs occurred before crossover will be summarized in the monotherapy group. All AE terms will be coded by Medical Dictionary for Regulatory Activities (MedDRA) Version 19.1 and will be presented by system organ class (SOC) and preferred term (PT). Treatment-emergent AEs will be summarized by SOC and PT and by CTCAE toxicity grade. The drug-related AEs, serious adverse events (SAEs) and drug-related SAEs, AEs leading to treatment discontinuation, dose delay and dose modification will be summarized by PT by CTCAE toxicity grade.

Death will be reported in a listing and summarized. A table will be provided for grade 5 AE and the relationship with any study drug.

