4.3 EARLY TERMINATION/SAFETY FOLLOW-UP VISIT

An early termination visit is required for any subjects who permanently discontinue study drug early for any reason including disease progression. Each subject should be followed for 30 (±7) days after his or her last dose of study drug (ie, the "safety follow-up visit") to monitor for resolution or progression of AEs (see Section 6.2.5) and to document the occurrence of any new events; unless, the subject receives a new anticancer therapy within this timeframe. Subjects who withdraw consent should still be encouraged to complete the safety follow-up assessments, but these assessments cannot be mandated once consent is withdrawn. The Schedule of Assessments (Appendix 5) describes the procedures required for the safety follow-up.

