6.2.1 Adverse Event Reporting Period

The AE reporting period for this study begins when the subject receives the first dose of study medication and ends with the safety follow-up visit (or last on-treatment visit if the safety follow-up visit is not done), or when the subject receives a new anticancer therapy. An exception to this reporting period is any AE occurring due to a protocol-defined screening procedure. Fatal AEs occurring within 30 days after the last dose of ACP-196 *AND* assessed by the investigator as related to ACP-196 must be reported as a SAEs.

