#### **6. ANALYSIS SETS**

## **6.1 All-Treated Population**

All-treated population is defined as all enrolled subjects who receive  $\geq 1$  dose of any study drug. All-treated population will be used for evaluating the safety and efficacy unless otherwise specified.

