### 10.6.2 Laboratory Abnormality

All of the laboratory tests are performed in central laboratory and/or in local laboratory. Analyses will be performed for laboratory test data collected at baseline and from first exposure to acalabrutinib to 30 days after last dose of acalabrutinib or up to the safety follow-up visit date, whichever is later. Laboratory test for hematology, serum chemistry, and T/B/NK cell count up will be performed in central laboratory with reference range and the results will be reported in standard international units or conventional units when appropriate. Applicable laboratory test results will be graded according to CTCAE Version 4.03 or higher. AMA (American Medical Association (AMA) Manual of Style 10th Edition 2017) laboratory values will be applied whenever reference ranges are not available (e.g., local laboratory data).

For selected laboratory test parameters, summary statistics (mean, standard deviation, median, minimum and maximum) will be produced at baseline, post-baseline values from the last visit, minimum and maximum post-baseline values, and changes of these post-baseline values from baseline. Post-baseline toxicity grade greater than baseline grade will be presented in the treatment-emergent laboratory abnormality table. Shift from baseline to the worst grade from first exposure to acalabrutinib to 30 days after last dose of acalabrutinib or up to the safety follow-up visit date, whichever is later, will be provided as shift tables for selected parameters.

To be included in the summary table, a subject must have at least one post-baseline value for the given time point.

- *Lymphocytosis*

Lymphocytosis is defined as an elevation in absolute lymphocyte count (ALC) of  $\geq 50\%$  compared to baseline and a post-baseline assessment  $>5 \times 10^9/L$  (Wang 2013). The number of subjects with at least one occurrence of lymphocytosis will be summarized. For subjects with lymphocytosis, resolution of lymphocytosis is defined as 1) a decrease of ALC value to the baseline level or lower, or 2) a decrease of ALC value that is below  $5 \times 10^9/L$ , whichever occurs first. Duration of lymphocytosis (DOL) is defined as the duration of time from the earliest date on which the ALC value met the lymphocytosis criteria at a post-baseline assessment to the earliest date on which a subsequent ALC value met the resolution criteria.

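### The TEAE window closes 30 days after the last acalabrutinib dose, although AEs are collected, and labs, vital signs and ECOG counted, up to a safety visit that may fall on day 37

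*SAP*

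**What the plan says.** SAP 10.6 limits the adverse event tables to treatment-emergent events: "Analyses of adverse events (AEs) will be performed on treatment-emergent AE (TEAE) data, unless otherwise specified". The window opens with an onset or "worsen date on or after the date of first dose of acalabrutinib" and closes "within 30 days following the last dose of acalabrutinib, whichever is later".

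The other safety windows are worded differently. SAP 10.6.2 takes laboratory data up to "30 days after last dose of acalabrutinib or up to the safety follow-up visit date, whichever is later". SAP 10.6.3 (vital signs) and 10.6.4 (ECOG) use the same two limits.

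The analysis population in SAP 6.1 names no particular drug. "All-treated population is defined as all enrolled subjects who receive" at least one "dose of any study drug. All-treated population will be used for evaluating the safety and efficacy unless otherwise specified".

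Protocol 6.2.1 says that AE collection "ends with the safety follow-up visit (or last on-treatment visit if the safety follow-up visit is not done"), or stops when new anticancer therapy is given. Protocol 3.1 and 4.3 place that visit 30 (±7) "days after his or her last dose of study drug", unless another cancer therapy has begun by then.

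**The concern.** The TEAE sentence asks for the later of two dates but supplies only one that can ever be later. The three sibling windows contain the missing limit, the date of the safety visit, so an omission is the natural explanation. As written, the rule would be programmed to day 30.

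Safety is the primary objective, and the TEAE tables are its main output. Protocol 6.1.1 requires a laboratory value that leads to treatment, discontinuation or dose modification to be reported as an AE. Suppose such a value first appears at a visit on day 35. It enters the treatment-emergent laboratory and shift tables under SAP 10.6.2, while the AE recorded for the same finding is not a TEAE. Two tables in one report would then disagree about one event.

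The second mismatch is the choice of drug. Protocol 3.2.1 and 6.2.2 attribute AEs to ACP-196, dexamethasone or both, and SAP 10.5.3 summarises exposure to each drug. The TEAE window follows acalabrutinib only.

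**Working it through.** The plan gives no figure for this point, so there is nothing to reproduce. Sample size and power are not involved. The check is date arithmetic.

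**Inputs**

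- TEAE window end: day 30 after the last acalabrutinib dose (SAP 10.6). Of the last dose (day 0) and day 30, day 30 is always later.
- Safety visit: V = 30 − 7 = 23 to 30 + 7 = 37 days after the last study drug (Protocol 3.1, 4.3).
- AE collection end: the safety visit, or new anticancer therapy (Protocol 6.2.1).
- L: days by which the last dexamethasone dose follows the last acalabrutinib dose. The documents give no value. L = 0 when acalabrutinib is the last drug taken or both stop together.

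**Formula**

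Days collected but outside the TEAE window = max(0, L + V − 30).

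**Certain case, L = 0 (either cohort)**

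- Visit on day 23: max(0, 23 − 30) = 0.
- Visit on day 30: max(0, 30 − 30) = 0.
- Visit on day 37: 37 − 30 = 7, that is, onset on days 31 to 37.

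**Conditional case, L > 0**

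This assumes that dexamethasone continues after acalabrutinib stops and that the visit is timed from the last dexamethasone dose. The documents state neither. The 28-day row uses the longest toxicity hold in Protocol 3.5.5.1; 7 and 14 days are illustrative.

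| L (days) | Visit day 23 | Visit day 30 | Visit day 37 |
|---|---|---|---|
| 0 | 0 | 0 | 7 |
| 7 | 0 | 7 | 14 |
| 14 | 7 | 14 | 21 |
| 28 | 21 | 28 | 35 |

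**After the fix**

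If the window closes at the later of day 30 after the last dose of any study drug and the visit date, the gap is 0 in every cell.

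**Start of the window**

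A subject who took only dexamethasone would belong to the All-treated population but would have no TEAE window at all, since both ends are set by acalabrutinib dates.

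**The case against.** A cut at 30 days after the last acalabrutinib dose is not foreign to these documents. Protocol 6.2.1 uses the same anchor for related fatal AEs, and the concomitant-medication windows in Protocol 4.1.4 and SAP 10.5.2 also stop 30 days after the last study drug. There may be a reason to treat laboratory data differently: the sample is drawn at the visit itself, so a strict day-30 cut would discard a scheduled measurement, whereas AEs are classified by onset. That reason is an inference; the SAP does not give it. Nor does it explain a sentence that asks for the later of two dates and omits one of them.

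The loss is also narrow. It needs an onset after day 30, a visit after day 30, and no new anticancer therapy in between. Deaths are listed and summarised in SAP 10.6 without a TEAE restriction. SAP 14.2.1 pulls some partial onset dates back to day 30, although complete dates after day 30 are not rescued. These limits stand, and the number of AEs affected cannot be estimated from the documents.

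A reader might infer that the gap reaches 35 days and falls mainly on dexamethasone-treated subjects. The documents do not support that as a finding. Table 3-1 acts on ACP-196 only, and Protocol 3.5.5.2 offers only a dose reduction for dexamethasone. But Protocol 3.5.5.1 also speaks of holding study drug and discontinuing study treatment, Protocol 3.8 withdraws subjects from study treatment, and Protocol 3.5.3.2 has the two drugs taken together. Dexamethasone alone is neither clearly permitted nor clearly ruled out. The synopsis also lists only ACP-196 as the study drug; on that reading the visit follows the last acalabrutinib dose and the gap stays at 7 days.

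**Conclusion.** The mismatch is real and small. Without any assumption about dexamethasone, up to 7 days of protocol-collected AEs (onset on days 31 to 37) fall outside the TEAE tables for subjects seen after day 30. This can happen in either cohort, and nothing is lost when the visit is on or before day 30. In the same subjects the laboratory, vital-sign and ECOG summaries do run to the visit, so outputs can conflict over one event.

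The drug anchor is a separate inconsistency: the population requires any study drug, the TEAE window acalabrutinib. If dexamethasone outlasted acalabrutinib by 7, 14 or 28 days and the visit fell on day 37 after it, the gap would be 14, 21 or 35 days, in combination and crossover subjects only. Those figures, and any heavier loss in dexamethasone-treated subjects, rest wholly on that assumption.

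Two other readings should be avoided. The All-treated population does not extend to the safety visit: it has no end date, and differs only in its anchor. The laboratory window is not fully tied to any study drug either: its 30-day limit also follows acalabrutinib, and only its visit limit extends it.

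**What to change.** In SAP 10.6, define a TEAE as an event with onset or worsening from the first dose of any study drug through the later of (a) 30 days after the last dose of any study drug and (b) the safety follow-up visit date, ending at the start of new anticancer therapy as in Protocol 6.2.1. State that study drug here means acalabrutinib or dexamethasone, so that the synopsis is reconciled with Protocol 3.2.1 and 6.2.2.

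Use the same anchor in SAP 10.6.2 to 10.6.4, and bring the cap on imputed AE start dates in SAP 14.2.1 into line with it.

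Adding the safety-visit limit to SAP 10.6 is one clause and by itself closes the certain 7-day gap. Re-anchoring the other sections means further short edits and minor reprogramming. TEAE counts may rise slightly. No new data are needed, and sample size and clinical management are unchanged.
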